### Recruitment.

Participants will be identified through a variety of sources. The Michigan Department of Health and Human Services (MDHHS) Michigan Tumor Registry collects information about cancer incidence, stage, and to a limited extent, the kinds of treatment that patients receive. These data are reported to the registry from various medical facilities. The Michigan Tumor Registry includes cancer case information received from the metropolitan Detroit Surveillance, Epidemiology, and End Results (SEER) registry. The Michigan Cancer Surveillance Program, which operates the Michigan Tumor Registry, is a member of the North American Association of Central Cancer Registries (NAACCR). The registry is certified by NAACCR as meeting all standards for quality, completeness, timeliness, and unresolved duplicate records and is estimated to be greater than 95% complete based on external audit findings. We will request Michigan Tumor Registry data for women diagnosed throughout the State of Michigan, even if they no longer reside in Michigan. Women will receive an introductory letter from the MDHHS describing the study and asking them to contact us if they are interested or if they would like to opt out of future mailings. A second letter will be sent to all women who do not respond within two weeks, and a final third letter to any non-responders from prior mailings two weeks after the second letter. Interested women from the Michigan database send their contact information to the MDHHS, who pass it along to the study team. We will also be recruiting from the Los Angeles Cancer Surveillance Program (the Los Angeles SEER) and our local University of Michigan Cancer Registry in a similar manner. After approval from the State of California

Cancer Registry IRB, they will provide contact information of potentially eligible women diagnosed with ovarian cancer and we will send them the same introductory letter being sent out by the MDHHS, a study flyer, and a brochure from the California Cancer Registry. A second letter will be sent to all women from Los Angeles who do not respond within two weeks, and a final third letter to any non-responders from prior mailings two weeks after the second letter. Interested women from Los Angeles will be able to contact the study team directly. The study team then performs a phone screen to determine eligibility with all interested women. We will also contact a randomly selected group of women from the LA SEER registry directly via phone and/or text message (SMS).

We will also recruit from the North Carolina Central Cancer Registry (NC CCR) and follow the same process as LA SEER; we will receive contact information from the NC CCR for potentially eligible women and continue with our 3 communication letters or direct phone call and/or text message (SMS). If we don't receive any response from text messages from women from the NC CCR, we may send up to three letters via mail.

We will utilize the UM Cancer Registry to identify potentially eligible women diagnosed with ovarian cancer and will send them the same introductory and consecutive 2nd and 3rd/final recruitment letters. We may utilize certified mail for the final recruitment mailing for all participants contacted via mail. For participants identified through the UM Cancer Registry we may choose to contact them via phone or text message (SMS) for recruitment. We will also reach out to the leadership at ovarian cancer survivor groups, including, but not limited to the Michigan Ovarian Cancer Alliance (MIOCA), Ovarian Cancer Research Alliance (OCRA), Facing Our Risk of Cancer Empowered (FORCE), Michigan Oncology Quality Consortium (MOQC), and Ovarian Cancer Canada. We will email a study flyer and a short description of the study to the contact person at these organizations to allow them to distribute this information to their members as they deem appropriate. Interested women will again be able to contact the study team, who will perform the same phone screen.

Additionally, we will utilize Michigan Institute for Clinical and Health Research (MICHR) services to provide social media advertisement support. MICHR will manage all IRB approved advertising. We may also choose to use the images and texts in the MICHR advertisements to advertise through U-M Rogel Cancer Center Social Media and Health Communications Core.

We will work with the Michigan Department of Communications to assist us to recruit via paid advertisement on website search engines.

We will post the study on researchmatch.org. Like UMHealthResearch, Research Match is a participant recruitment and feasibility analysis tool for researchers at participating institutions, University of Michigan is a participating institution. We will post our study information here as well for potential participants to learn more and to enroll.

Social media accounts may be created to help recruit participants and guide them to our study. A detailed recruitment portfolio which includes imagery and text can be found in section 8-1.8 of our application.

We may choose to work with BuildClinical to help accelerate enrollment. BuildClinical is a health technology company that enables academic researchers to accelerate their clinical research patient recruitment efforts by engaging the exact population needed through digital advertising and ultimately reducing the patient access and awareness gaps that exist today.

We may choose to utilize the DataDirect resource at U-M to help identify potentially eligible participants. DataDirect is available for faculty researchers and their study team members to access both discrete variables and free-text string data from the electronic medical record (EMR).

Snowballing: We may choose to email participants who have completed study, and share our flyer and social media content with them. If they would like to, they may share our study information to their own personal accounts or groups that they may be members of.

### **3.2 Randomization.**

The biostatistician will provide sealed envelopes for the randomization of all participants. Participants will be

randomized to one of the three study arms: Acupressure, Sham acupressure or Control. A random generator for block stratified randomization in blocks of 6 participants will be programmed by [name], the study statistician. Eligible patients will be randomized into one of three groups - relaxing acupressure, sham acupressure, or no treatment - in a 1:1:1 ratio for a total of 171 participants with 57 randomized into each group.

We will be delivering our self-acupressure interventions (relaxing and sham) using our modified MeTime Acupressure mobile app. We will rename the MeTime Acupressure app to "Study App" and change the icon so participants will not be able to locate it in the Apple or Google Play Stores and unblind themselves. In association with the 3D Media Lab at the University of Michigan we will create a mobile app for our sham acupressure points. The sham and relaxing acupressure apps will be identical in all aspects except for the acupoint locations. For women randomized into the "no treatment arm" they will receive the acupressure app and AcuWand at the end of their study participation. The acupressure app will be loaded onto computer tablets by our computer information technology (IT) support person. Women in the acupressure arms will also receive an AcuWand to be used in association with the acupressure app to help women apply the correct amount of pressure to acupoints. The women will receive directions within the acupressure app on how to use the AcuWand. The AcuWand has been designed to use two lithium-ion long lasting (up to one year with normal use) batteries. Participants are asked to return the AcuWand with provided materials at no cost to them in order to upload data about frequency, duration and amount of pressure of acupressure applications. Of note: no Wi-Fi connection is needed to use the acupressure app and our IT support person will be available to help participants who are unfamiliar with or have any issues with their tablet, AcuWand or the app.

**Relaxing Acupressure.** There are 5 acupoints with 4 of the acupoints performed on both the left and right sides of the body (total of 9 points to stimulate; see Figure 7). Each of the 9 acupoints will be stimulated for 3 minutes per point

with the AcuWand giving a total treatment time of 27 minutes daily. The relaxation acupoints are:

- *Yin tang* (Unilaterally): forehead, between eyebrows
- *Anmian* (EX17) (Bilaterally): posterior aspect of the neck
- Heart 7 (HT7) (Bilaterally): palmer surface of the hands on the wrist crease
- Spleen 6 (SP6) (Right and Left/bilaterally): inside of the lower leg
- Liver 3 (LV3) (Bilaterally): foot

The relaxing points were selected based on existing data showing their effectiveness for treating fatigue.

[figure not shown]

Figure 7

**Sham Acupressure.** Sham acupoints were chosen by [name] in locations where no known acupoints exist. There are 5 acupoints with 4 of the acupoints performed on both the left and right sides of the body (total of 9 points to stimulate; see Figure 7). None of these points are on meridians nor are they near actual points (at least one inch away from meridians and points). They were chosen to be in the same general body quadrant as the relaxation points. Each of the 9 acupoints will be stimulated for 3 minutes per point giving a total treatment time of 27 minutes daily. The sham acupoints are:

- Pressure Point #1 (Unilaterally): This point is located on the side of the head, above the right ear.
- Pressure Point #2 (Bilaterally): This point is located on the muscle of the upper arm. Located in the middle point directly between the crease of the elbow (when arm is flexed) and the shoulder muscle one finger width toward the biceps muscle.
- Pressure Point #3 (Bilaterally): This point is located on the upper thigh muscle on the lateral side of the leg.
- Pressure Point #4 (Bilaterally): This point is located on the lower thigh muscle on the lateral side of the upper leg.
- Pressure Point #5 (Bilaterally): This point is located on the lateral side of the lower leg and is located midway between the line connecting the outer ankle bone and the knee.

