### 3.3 Blinding.

Our IT support person will place the computer tablets—already loaded with either the acupressure app--sham or relaxing--or the “no treatment” message and the AcuWands into opaque shipping boxes per our randomization code, i.e., a tablet with the sham acupressure app loaded on it would be placed in a shipping box labeled with a study ID assigned to the sham arm. The outside of the shipping boxes will be labeled with study IDs. This will ensure that only our IT support person will be unblinded, but all study staff and researchers will remain blinded until after the completion of data analyses. The IT support person will not be responsible for collecting or analyzing any study data. Participants in the “no treatment” arm will not be blinded; however, the two self-acupressure arms will be blinded as to which acupressure treatment they have been randomized. The MeTime app will be re-named to “Study App” for the study.

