**Safety, Fidelity, Blinding and Adherence (administered week 6 except for adverse events and adherence to acupressure, which are collected throughout the study).**

Adverse Events will be graded according to National Cancer Institute Common Toxicity Criteria version 4.03.

Testing Participant Fidelity We will be assessed using two methods. The first, as detailed in our prior study, is done by research staff using a Skype face-to-face call (we will install Skype on the computer tablets and assist participants in using this program as needed.) Participants will be asked to identify the location, stimulation technique, and the amount of pressure (be able to demonstrate correct use of their AcuWand) of their acupoints. The number of acupoints correctly located will be recorded as will the adequacy of stimulating the acupoints (recorded as "yes" or "no"). The percentage of correct answers 0 to 100% will be calculated, based on circular (clockwise or counterclockwise) motion, maintaining contact with skin, and applying pressure such that the nail of the applying finger/thumb blanches. The second method will be data download from the AcuWand via Bluetooth when the computer tablet is connected to Wi-Fi. The AcuWand will be able to provide data on the duration, frequency, and amount of pressure used by participants-it cannot provide data on the location of where participants stimulated their points. We employ both methods to ensure that fidelity is measured across all parameters and in collect redundant measure in case an AcuWand does not transmit data.

Blinding will be assessed by asking participants, which type of acupressure they thought they were performing.

Adherence to Acupressure will be assessed by asking participants to record if and when they performed acupressure, the order in which they performed their acupressure points, and the amounts of achiness and/or tenderness they experienced while performing the acupressure on a Visual Analog Scale daily in the study logbooks. These will be used in association with data downloaded from the AcuWands. Bi-weekly emails will be used to troubleshoot and encourage adherence.

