## 8.0 DATA MANAGEMENT

Study measures will be delivered electronically to participants using RedCAP. RedCAP is a generalized survey service supported by the University of Michigan Medical School permitting the creation and distribution of surveys, as well as data storage and analysis. RedCAP is user-friendly but can handle complex designs. For instance, simple surveys can be produced in minutes. Complex studies, involving randomization and embedded and longitudinal data, are also possible. RedCAP is also HIPAA compliant. RedCAP surveys will be accessed by the participant through an electronic device, via e-mail link forwarded from the study team, and are separate from the acupressure app. Those unable to effectively access and use these instruments will have a study team member administer these measures via phone, entered directly into RedCAP.

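### One fixed block size of 6, printed in the protocol, with an open no-treatment arm and undescribed envelope custody, could let staff identify up to about 29% of assignments in advance as acupressure or no treatment

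*Combined protocol and SAP*

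**What the plan says.** Section 3.2 (Randomization) sets out the mechanism: "The biostatistician will provide sealed envelopes for the randomization of all participants". It continues: "A random generator for block stratified randomization in blocks of 6 participants will be programmed by" the study statistician. Allocation is "in a 1:1:1 ratio for a total of 171 participants with 57 randomized into each group". Only one block size is given. The design is called stratified, but no factor is named, and custody and opening of the envelopes are not described.

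Section 3.3 (Blinding) says of the no-treatment group that this "arm will not be blinded; however, the two self-acupressure arms will be blinded". The IT support person packs the opaque boxes, labelled with study IDs, according to the randomization code. The stated result is that "only our IT support person will be unblinded, but all study staff and researchers will remain blinded until after the completion of data analyses".

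Other sections describe contact between staff and participants after randomization:

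- Section 4.1 (Safety, Fidelity, Blinding and Adherence): the first fidelity check, at week 6, "is done by research staff using a Skype face-to-face call", and participants show where their points are. Also, "Bi-weekly emails will be used to troubleshoot and encourage adherence".
- Section 10.3.1 (Guidelines): staff show participants how hard to press at the start of the study, and the team later telephones and asks about bruising. The Risk Assessment in section 1.0 gives the first of these tasks to the app instead.
- Section 3.1 (Recruitment): the study team telephone-screens all interested women. Table 1 includes criteria that need judgement, such as medical stability and planned changes of therapy.

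**The concern.** With a known fixed block size, anyone who can follow the sequence knows what is left at the end of each block. Concealing the envelope contents does not prevent this if earlier assignments become known. Here part of each assignment is open by design: a woman in the no-treatment arm knows her arm, and a conversation about pressure, bruising or acupoints tells staff whether she is doing acupressure.

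If someone who screens can foresee that the next place is acupressure or no treatment, judgement about eligibility or the timing of enrolment can be influenced, even unintentionally. The result would be selection bias between the no-treatment arm and the acupressure arms. That bears on relaxing acupressure versus no treatment, one of the two comparisons in the primary aim, and the outcome is self-reported. Covariate adjustment could address only differences that were measured, so this is better prevented than analysed away.

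**Working it through.** **Inputs.** From section 3.2: block size 6, ratio 1:1:1, 171 women, 57 per arm. Each block therefore holds 2 no-treatment (N) and 4 acupressure (A) places. Assumptions not in the documents: a single stratum, and staff who know the block size, where each block starts, and the N or A status of earlier women.

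**The plan's own figure.** 3 × 57 = 171. With 150 completers, 1 − 150/171 = 12.3% loss, consistent with the stated dropout of roughly 13%. The documents give no figure for predictability.

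**Upper bound per block.** The remaining places are certain once both N or all four A are used.

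- Expected places after the last N: 4 A spread over 3 gaps = 4/3.
- Expected places after the last A: 2 N spread over 5 gaps = 2/5.
- Sum: 4/3 + 2/5 = 26/15 = 1.733 of 6 = 28.9%.

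By position in the block, the probability of certainty is 0, 0, 1/15, 3/15, 7/15 and 1, which also sums to 26/15.

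**Over the whole trial.** There are 28 full blocks plus 3 places: 28 × 26/15 + 1/15 = 729/15 = 48.6 of 171 = 28.4%.

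**What would be known.** (4/3)/6 = 22.2% certainly acupressure, type unknown; (2/5)/6 = 6.7% certainly no treatment. The exact arm is known only for the 6.7%.

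**Delayed knowledge.** Each assignment not yet known shifts the position probabilities one place later:

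- last 1 unknown: (1/15 + 3/15 + 7/15)/6 = 12.2%
- last 2 unknown: (1/15 + 3/15)/6 = 4.4%
- last 3 unknown: (1/15)/6 = 1.1%
- last 4 or more unknown: 0%

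**Partial knowledge.** If each earlier status is known with probability q, the share is (4q²/3 + 2q⁴/5)/6. For q = 0.75: (0.750 + 0.127)/6 = 14.6%. For q = 0.50: (0.333 + 0.025)/6 = 6.0%.

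**Other block schemes, still with full and immediate knowledge.** A larger fixed and known block helps only moderately: size 9 gives (6/4 + 3/7)/9 = 21.4%, and size 12 gives (8/5 + 4/9)/12 = 17.0%. Sizes drawn at random with equal probability, where staff know the possible sizes but not the realised ones, were simulated over 171 women: 3/6/9 gives 3.9% and 6/9 gives 5.3%, against 28.4% for fixed blocks of 6.

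**57 per arm.** 171/6 = 28.5. Twenty-eight blocks give 56 per arm, and three places come from an open block. The chance of one per arm is (2 × 2 × 2)/20 = 40%; otherwise the split is 58/57/56 in some order. For the 58 versus 56 comparison, (1/58 + 1/56)/(2/57) = 1.0003, so the variance rises by about 0.03%.

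**The case against.** The strongest reply is that section 3.3 limits knowledge of the arm to the IT support person, uses opaque boxes labelled by ID, and sends every arm a tablet. Section 3.0 gives all groups the same number of contacts. Sealed envelopes and fixed blocks are recognised methods, and nothing suggests that staff would steer enrolment.

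Timing also matters. Randomization happens in the screening phase, whereas the fidelity call is at week 6. If that call were the only route, the full 29% would need evenly spaced entries at least 6 weeks apart: 170 × 6 = 1,020 weeks, about 20 years. If the adherence emails are fortnightly and the first reveals the arm, it would need 170 × 2 = 340 weeks, about 6.5 years. Only the pressure demonstration at the start, in section 10.3.1, would disclose quickly, and section 1.0 assigns that to the app. The enrolment rate is not given.

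Much of this stands, and it rules out several stronger readings that a reader might infer:

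- That the design makes 29% of assignments predictable. This is only the top of a range that reaches 0%.
- That recruiting staff are known to be unblinded. The documents do not say that those who make the calls or send the emails also screen.
- That only acupressure women have logbooks, adherence emails or fidelity calls. This is plausible, but Table 2 does not split these by arm.
- That the blinded comparison of relaxing with sham is exposed. It is not.

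What the reply does not answer is that equal numbers of contacts do not conceal their content, and that the plan asserts staff blinding without saying how it survives contact with an open arm.

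**Conclusion.** The point holds as a weakness in allocation concealment for acupressure versus no treatment. A fixed printed block size, unstated envelope custody and an open arm are combined with staff contacts that sections 3.3, 4.1 and 10.3.1 leave unreconciled, and no separation between those staff and the screening team is described.

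The size is between 0% and 28.9% of assignments. The upper end rests on a single stratum, knowledge of the block size and boundaries, and every earlier status being known before the next entry. A delay of one assignment already brings it to about 12%. The figure counts only assignments known with certainty, and it is a measure of opportunity: the documents contain no evidence that allocation has been or would be subverted.

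That the list does not guarantee 57 per arm is a wording matter. The likely imbalance without strata, 58/57/56, has negligible effect on power.

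**What to change.** For women not yet randomised:

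1. Generate the list with block sizes that vary at random in multiples of 3, for example 3, 6 and 9, and keep the sizes out of documents available to recruiting staff. In the simulation this cuts the worst case from about 28% to about 4%.
2. Release each assignment only after eligibility and consent are locked, by someone outside recruitment, such as the already unblinded IT support person, or by a central system if one is available. Section 8.0 says of the survey platform only that "Complex studies, involving randomization and embedded and longitudinal data, are also possible". That is a general description, not evidence of a configured allocation module, so its availability would need to be confirmed.
3. State who holds and opens the envelopes if they are kept, and name the stratification factors or delete the word.
4. Reconcile sections 1.0, 3.3, 4.1 and 10.3.1 on which staff can learn acupressure status, and keep those staff apart from screening where feasible.
5. Write approximately 57 per arm.

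The cost is a re-programmed list, a short amendment and slightly less exact balance at any moment. Setting up a central system would add some work; release through the IT support person would add little.

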### 3.3 Blinding.

Our IT support person will place the computer tablets—already loaded with either the acupressure app--sham or relaxing--or the “no treatment” message and the AcuWands into opaque shipping boxes per our randomization code, i.e., a tablet with the sham acupressure app loaded on it would be placed in a shipping box labeled with a study ID assigned to the sham arm. The outside of the shipping boxes will be labeled with study IDs. This will ensure that only our IT support person will be unblinded, but all study staff and researchers will remain blinded until after the completion of data analyses. The IT support person will not be responsible for collecting or analyzing any study data. Participants in the “no treatment” arm will not be blinded; however, the two self-acupressure arms will be blinded as to which acupressure treatment they have been randomized. The MeTime app will be re-named to “Study App” for the study.

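### Section 3.3 says only the IT person is unblinded, but staff who score acupoint location at week 6 necessarily learn the arm

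*Combined protocol and SAP*

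**What the plan says.** Section 3.3 makes two universal statements: "only our IT support person will be unblinded", and "all study staff and researchers will remain blinded until after the completion of data analyses". The IT person is barred from collecting or analysing data; no such separation is written for anyone else. Section 4.0 gives a control that can be blinded to participants and staff as a reason for including the sham arm, so staff blinding is a stated feature of the design.

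Section 4.1, in the paragraph on testing participant fidelity, describes the first of two fidelity methods. It "is done by research staff using a Skype face-to-face call". On that call, "Participants will be asked to identify the location, stimulation technique, and the amount of pressure", and then "The number of acupoints correctly located will be recorded as will the adequacy of stimulating the acupoints". Table 2 places this at week 6.

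Section 3.2 says of the two apps: "The sham and relaxing acupressure apps will be identical in all aspects except for the acupoint locations". On allocation, the study statistician programs the blocked sequence, and "The biostatistician will provide sealed envelopes for the randomization of all participants".

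Section 8.0 makes electronic self-report in RedCAP the rule. Women who cannot use the electronic forms "will have a study team member administer these measures via phone, entered directly into RedCAP".

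**The concern.** The sham arm allows a relaxing-versus-sham comparison free of expectation effects. Women in those two arms do not know which they received, and the plan says the staff around them do not know either. If staff do know, three things are at risk.

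First, a report that repeats section 3.3 would claim a safeguard the trial did not fully have.

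Second, anyone who knows the arm and then speaks to a participant can cue her, even unintentionally. This could affect a survey given by phone at week 6, 12 or 24. It could also affect her answer to the question about which acupressure she thought she was doing, which is the only check of the blind in the plan.

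Third, adverse-event relatedness is a judgement, and under section 5.3 events judged unrelated or unlikely to be related are not reportable. The plan does not keep people who know the arm from making that judgement.

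**Working it through.** The plan gives no figure to reproduce here. The main check is a comparison of sections, followed by a short calculation of size.

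**Step 1: does the rater learn the arm?** The point lists in section 3.2 differ visibly:

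| | Relaxing | Sham |
|---|---|---|
| Head and neck | forehead, back of neck | side of head above right ear |
| Arm | wrist crease | upper arm |
| Leg and foot | inner lower leg, foot | upper and lower lateral thigh, lateral lower leg |

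To count correctly located points, the rater needs the map for that woman's arm. Even a rater who had not been told the arm would see it when the woman touched her forehead rather than the side of her head. Scoring location and staying blind to arm are incompatible. The second fidelity method, the AcuWand download, does not have this problem: section 4.1 says it records no location.

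**Step 2: how many women?** Section 3.2 gives 57 per arm and 171 in total. Acupressure participants number 57 + 57 = 114, and 114 / 171 = 67%. This is an upper limit, since not every woman need complete the call.

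**Step 3: when?** Table 2 puts the BFI, the blinding question and the fidelity assessment in the same week-6 column, with a window of 2 days before to 5 days after. No order is given. If the surveys and blinding question come first, the call cannot affect them. If the call comes first, it can. Contacts at weeks 12 and 24 follow it in any case.

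**Step 4: the allocation list.** Section 3.2 gives the sequence to the statistician and the envelopes to the biostatistician. At least one researcher besides the IT person therefore creates the allocation, which does not fit the word *only* in section 3.3. The documents do not say whether the list uses coded arms, who keeps it, who opens the envelopes, or who analyses the data.

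**Step 5: how large could the effect on BFI be?** The documents give neither the share of surveys done by phone nor any size for cueing. Assume a phone share of 10 to 20%, a cueing effect of 0.5 BFI points in one arm, and that every phone survey is given by someone who knows the arm.

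- Shift in arm mean = phone share × cueing effect.
- Low end: 0.10 × 0.5 = 0.05. High end: 0.20 × 0.5 = 0.10.
- Planned relaxing-versus-sham difference at end of treatment (section 9.0): 3.5 − 2 = 1.5.
- Relative size: 0.05 / 1.5 = 3.3% and 0.10 / 1.5 = 6.7%.
- If both arms were cued equally in opposite directions, the difference would shift by twice as much, 0.10 to 0.20, or 6.7% to 13.3% of the planned difference.

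**The case against.** The strongest reply is that the conflict is real but narrow. Opaque boxes, study-ID labels and a separate IT person still operate. By this route staff learn the arm only at week 6, after treatment. The primary outcome is self-reported, normally without staff involvement. For the week-6 comparison to be biased, a survey would have to be given by phone, after the call or with knowledge from it, by someone who knows the arm and cues in one direction. No section says that chain occurs. This stands, and it is why the likely bias is put as small.

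Three stronger readings are tempting, and the reply is right to resist them:

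- **The analyst is unblinded because the statistician makes the list.** Preparing a sequence and sealed envelopes is ordinary practice and compatible with a blinded analysis, if arms are coded or someone else analyses. The plan says neither, so this is a gap and not proof.
- **Unblinded raters judge adverse events and give phone surveys.** Section 5.5 lists attribution as a data element without naming an assessor; section 5.3 has the principal investigator review non-serious events. Section 8.0 says only that a study team member makes the phone calls. The plan neither assigns these tasks to fidelity raters nor bars them.
- **A woman with no fidelity call is thereby known to be in the no-treatment arm.** Section 3.0 promises equal contacts in all groups, and an acupressure participant may miss her call. Participants in the no-treatment arm are in any case openly unblinded.

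None of this rescues the sentence in section 3.3, which allows no exception beyond the IT person.

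**Conclusion.** The concern holds. As written, section 3.3 cannot be true together with section 4.1: fidelity raters learn the arm of each acupressure participant they assess, up to 114 women. It also fits poorly with the allocation roles in section 3.2. This conclusion rests on the documents' text alone and on no numerical assumption.

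A reader might go further and infer that staff and researcher blinding does not exist at all, or that the primary result is compromised. The documents support neither. They show that the raters and whoever creates the list fall outside the stated blind, not that every staff member does. Blinding of participants between the two acupressure arms is not in question. The illustrative BFI shift of 0.05 to 0.10 (up to 0.20 in the difference if both arms are cued in opposite directions) depends wholly on the assumed phone share and cueing effect. It is small against 1.5.

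What remains is a misstated safeguard, an unspecified order of tasks at the primary time point, and avoidable exposure in phone-administered surveys, the blinding question and later contacts if raters carry them out.

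**What to change.** 1. Restate section 3.3: the two acupressure arms are blinded to each other; the IT person, the fidelity raters (from the week-6 call) and whoever prepares the allocation list are unblinded.
2. In section 4.1 and Table 2, require the week-6 surveys and the blinding question to be submitted before the fidelity call.
3. Where existing staffing allows, have someone other than a woman's fidelity rater give her phone-administered outcomes and assess adverse-event relatedness. Staff numbers are not stated, so this is conditional.
4. Analyse with coded arm labels, with the key held by the IT person until analyses are final. Section 3.3 already has that person pack boxes by the randomization code. For this to work, the analyst must not be able to match the labels to the list, so either the sequence is written in neutral codes or the list preparer does not analyse.

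The cost is revised wording, a fixed task order and a small scheduling constraint at week 6, plus a less favourable description of blinding. No visit, sample size or model changes. Coding will mainly protect relaxing versus sham, because the no-treatment arm is likely to be recognisable from its lack of acupressure data.
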